11.4.2.7 Reporting of action taken with study treatment

The Investigator must report the action taken with study treatment using the definitions below and record it on the AE Log of the eCRF:

Dose increased

Dose not changed

Dose rate reduced

Dose reduced

Drug interrupted

Drug withdrawn

Not applicable

Unknown

11.4.2.8 Collecting adverse events

AEs identified using any of the following methods will be recorded:

- AEs spontaneously reported by the subject

- AEs observed by the Investigator or medical personnel
- AEs elicited based on non-leading questions from the Investigator or medical personnel

11.4.2.9 Recording adverse events

AEs must be recorded in the AE Log of the eCRF. The Investigator must provide information on the AE, preferably with a diagnosis or at least with signs and symptoms; start and stop dates, start and stop time; intensity; causal relationship to IP or study procedures; action taken, and outcome.

If the AE is serious, this must be indicated in the eCRF.

AEs, including out-of-range clinically significant clinical safety laboratory values, must be recorded individually, except when considered manifestations of the same medical condition or disease state; in such cases, they must be recorded under a single diagnosis.

Malfunctions/incidents with the e-cigarette system will be reported to the Sponsor on a separate Product Form.

11.4.2.10 Reporting of serious adverse events

SAE reporting should be performed by the Investigator within 24 hours of awareness via the eCRF. All available information regarding the SAE should be entered in the AE Log for the specific subject. By saving the event as “serious” in the eCRF and once the Investigator has signed-off of the event, an e-mail alert is automatically sent to predefined recipients to highlight that an SAE has been registered. The same information is automatically sent to [contact].

The SAE report is reviewed by a designated person at CTC’s Pharmacovigilance (CTC PV) department to ensure that the report is valid and correct. For fatal or life-threatening SAEs where important or relevant information is missing, immediate follow-up is undertaken and queries to the site are raised. Investigators or other site personnel should inform CTC PV of any follow-up information on a previously reported SAE immediately but no later than the end of the next business day of when he or she becomes aware of it.

If the SAE report in the eCRF is updated, a new e-mail alert will be sent.

If any additional documentation is required (e.g. autopsy report), CTC PV will request this information from the study site.

In case the eCRF cannot be accessed, the SAE should be reported by manual completion of the paper SAE Form, provided in the Investigator Site File (ISF). The completed, signed and dated paper SAE Form should, within 24 hours, be scanned and e-mailed to:

[REDACTED]
[REDACTED]
[REDACTED]

A copy of the paper SAE form must also be e-mailed to CTC at: [contact].

The study site should notify the site Monitor via phone or e-mail about the submission of the SAE report. As soon as the site personnel have access to the eCRF, the SAE should be reported electronically as well.

The Sponsor or delegate will assume responsibility for reporting SAEs to the independent ethics committee (IEC) in accordance with local regulations.

11.4.2.11 Treatment and follow-up of adverse events

Subjects with AEs that occur during the study must be treated according to daily clinical practice at the discretion of the Investigator.

AEs must be followed up until resolution or to the end-of-study visit, whichever comes first. At the end-of-study visit, information on new AEs, if any, and stop dates for previously reported AEs must be recorded (if known). AEs assessed as stable by the Investigator at the end-of-study visit will not have to be followed up until resolution.

It is the responsibility of the Investigator to follow up on all SAEs until the subject has recovered, stabilised, or recovered with sequelae, and to report to the Sponsor all relevant new information using the same procedures and timelines as those for the initial report. Relevant information includes discharge summaries, autopsy reports, and medical consultation.

11.4.2.12 Procedures in case of pregnancy

In case of pregnancy or suspicion of possible pregnancy of any female subjects, the study treatment must be stopped immediately, and the subject discontinued from participation in the study. Pregnancy itself is not regarded as an AE unless there is a suspicion that the IP may have interfered with the effectiveness of the contraceptive medication. However, the outcome of all pregnancies (spontaneous miscarriage, elective termination, normal birth or congenital abnormality) must be followed up and documented even after the subject was discontinued from the study.

All events of congenital abnormalities/birth defects are SAEs. Spontaneous miscarriages should also be reported and handled as AEs. All outcomes of pregnancy must be reported to the Sponsor and the Principal Investigator on the pregnancy outcomes report form.

11.4.2.13 Treatment of overdose

An overdose is a dose in excess of the dose specified for each cohort in this clinical study protocol (CSP).

Over-dosing is not likely to occur in this study since all IP will be administered by site personnel under medical surveillance. In cases of accidental overdose, standard supportive measures should be adopted as required.

An overdose should be documented as follows:

- An overdose with associated AE is recorded as the AE diagnosis/symptoms in the AE Log of the eCRF.
- An overdose without associated symptoms is only reported in the subject's medical records.

11.4.3 *Vital signs*

Systolic and diastolic blood pressure and pulse will be measured in supine position after 10 minutes of rest.

Vital signs will be judged as normal, abnormal, not clinically significant or abnormal, clinically significant. The assessment will be recorded in the eCRF.

Post-IP vital signs, where the change from the values measured at the screening visit is judged as “abnormal, clinically significant” by the Investigator will be reported as AEs.

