At Visit 2, subjects will arrive to the clinic in the morning of Day 1 and will remain at the clinic until the afternoon. Day 1 will contain pre-PET safety assessment, preparation for the PET assessments (including insertion of an arterial catheter), two PET assessment sessions with at least 2 hours between the sessions and safety follow-up (including removal of arterial catheter) after the second PET assessment.

The subjects will have breakfast (optional) at the research clinic before the first PET-session. Lunch will be served at the research clinic between the two PET-sessions.

The subjects will be carefully monitored by clinical staff during and after the PET-sessions. There is immediate access to equipment and qualified staff in case of emergency.

A final End-of-Study phone call (Visit 3) will take place on Day 7 (± 2) or after early withdrawal to follow up on safety (AEs and concomitant medications).

Methodology – PART B

In PART B of the study, two different formulations of [¹¹C]nicotine will each be given to 2 subjects. The subjects will have one PET-assessments each (PET 3) after two inhalations of [¹¹C]nicotine via the *myblu*TM.

PART B will be completed for 2 subjects on each formulation before a decision will be taken if 3 additional subjects should be added to PART B. The decision is based on whether the results from the first scans show significant, quantifiable uptake of radioactivity in the brain. If 3 additional subjects are included, they will be treated with the formulation that showed the best uptake profile.

The IP will be given as inhalation (“puffs”) via the *myblu*TM e-cigarette system to obtain a tracer dose of up to 50 MBq.

Subjects will come for 2 visits to the clinic, 1 MRI assessment visit and have 1 End-of Study follow-up telephone call (Visit 3).

Screening (Visit 1) will take place from Day -28 to Day -1 and will include an eligibility check, review of health status and inhalation training.

At Visit 2, subjects will arrive to the clinic in the morning of Day 1 and will remain at the clinic until the afternoon. Day 1 will contain pre-PET safety assessments, preparation for the PET assessments (including insertion of an arterial catheter), one PET assessment session and safety follow-up (including removal of arterial catheter) after the PET assessment.

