The subjects will have breakfast (optional) at the research clinic before the PET-session. Lunch (optional) will be served at the research clinic after the PET session.

The subjects will be carefully monitored by clinical staff during and after the PET-session. There is immediate access to equipment and qualified staff in case of emergency.

A final End-of-Study phone call (Visit 3) will take place on Day 7 (± 2) or after early withdrawal to follow up on safety (AEs and concomitant medications).

During the study period, the subjects will also have an MRI-scan. The MRI can be performed at any suitable timepoint during the study after the screening visit until the End-of-Study-visit.

Investigational Product (IP), dosage and mode of administration

The IPs will be supplied as the *myblu*TM e-cigarette system with e-liquid pods:

The *myblu*TM e-cigarette will be supplied together with a USB charger.

E-liquid pods will be supplied as:

- Pods for training purposes, containing 2.5% freebase nicotine formulation (no flavour) corresponding to Formulation 1.
- Pods for training purposes, containing 2.5% nicotine salt formulation (no flavour) corresponding to Formulation 2.
- Empty pods (for filling at the PET Centre with radiolabelled Formulation 1 and Formulation 2)

Bulk liquid Formulation 1 and Bulk liquid Formulation 2, will be supplied, for radiolabelling and filling of empty e-liquid pods at the PET Centre.

Duration of treatment

1 day

Duration of each subject's involvement in the study

Each subject is expected to participate in the study for approximately 7 days from the day of PET-session (Day 1, Visit 2) to the End-of Study Visit. The Screening Visit will be performed within 28 days prior to PET-scanning (Day -28 to Day -1).

PET assessment

PET DICOM images over the lungs and oral cavity (PART A) and brain (PART B). Radioactivity vs. time profiles for arterial blood after administration of [¹¹C]nicotine

Safety assessments

AEs

Vital signs

Statistical methods

No formal sample size calculation has been performed for this study. The proposed sample size is considered sufficient to provide adequate information for the study objectives.

Continuous data will be presented in terms of evaluable and missing observations, arithmetic mean, standard deviation (SD), median, minimum and maximum value. Categorical data will be presented as counts and percentages. When applicable, summary data will be presented by

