8 STUDY DESIGN

8.1 Overall study design and schedule of events

This is a single centre, exploratory PET-study of deposition, disposition and brain uptake of [¹¹C]nicotine when given to smokers as two different formulations via the *myblu*TM e-cigarette system.

The study is divided in two parts:

PART A: PET 1 and PET 2 (including 5 subjects/formulation, total 10 subjects)

PART B: PET 3 (including 2 subjects/formulation + 3 optional subjects, total 4-7 subjects)

An overview of the study design is shown in Figure 8.1-1.

[figure not shown]

Figure 8.1-1 Overview of the study design

8.1.1 PART A: PET 1 and PET 2

In PART A of the study, two different formulations of [¹¹C]nicotine will each be given to 5 subjects. The subjects will have two PET-assessments each (PET 1 and PET 2) after inhalation of [¹¹C]nicotine via the *myblu*TM during the same treatment day. PART A will be completed for 5 subjects on each formulation before initiation of PART B.

The IP will be given as inhalation (“puffs”) via the *myblu*TM e-cigarette system to obtain a tracer dose of up to 25 MBq/PET-session.

Subjects will come for 2 visits to the clinic and have 1 End-of Study follow-up telephone call.

Screening (Visit 1) will take place from Day -28 to Day -1 and will include an eligibility check, review of health status and inhalation training, see Table 8.1-1 for details.

At Visit 2, subjects will arrive to the clinic in the morning of Day 1 and will remain at the clinic until the afternoon. Day 1 will contain pre-PET safety assessment, preparation for the

PET assessments (including insertion of an arterial catheter), two PET assessment sessions with at least 2 hours between the sessions and safety follow-up (including removal of arterial catheter) after the second PET assessment.

The subjects will have breakfast (optional) at the research clinic before the first PET-session. Lunch will be served at the research clinic between the two PET-sessions.

The subjects will be carefully monitored by clinical staff during and after the PET-sessions. There is immediate access to equipment and qualified staff in case of emergency.

A final End-of-Study phone call (Visit 3) will take place on Day 7 (± 2) or after early withdrawal to follow up on safety (AEs and concomitant medications).

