Each subject is expected to participate in the study for approximately 7 days from the day of PET-sessions (Day 1, Visit 2) to the End-of Study Visit. The Screening Visit will be performed within 28 days prior to PET-scanning (Day -28 to Day -1).

The schedule of events is shown in Table 8.1-1.

Study assessments are described in Section 11.

Table 8.1-1 Schedule of events PART A

Visit	Refer to CSP section:	Visit 1 Screening	Visit 2 ⁰					Visit 3 End-of- study
			Day -28 to Day -1	Admission 08:00	10:00	12:00	14:00	
Assessment/ Approximate timepoints								Phone call Day 7 (±2) ²
Informed Consent	14.3	X						
Inclusion/exclusion criteria	9.4, 9.5	X		X ³				
Demographics	11.2	X						
Medical/surgical history	11.2.5	X						
HIV, hepatitis B and C	11.2.7	X						
Alcohol breath test	11.2.9	X		X				
Urine Drug Screen	11.2.8	X		X				
Weight/height (Body Mass Index [BMI])	11.2.4	X						
Physical Examination	11.2.12	X						
Clinical Laboratory Profile	11.2.11	X						
Vital Signs	11.4.3	X						X
12-lead ECG	11.2.13	X						
Inhalation training	11.3.1	X		(X)				
Modified Allen test	11.3.2	X		X				
Insertion of arterial catheter	11.3.2			X				
PET assessment ⁴	11.2.11				X			X
Sampling arterial blood for radioactivity assessment ⁴	11.2.11				X			X
IP administration ⁴	10.5				X			X
Meals at the research clinic	9.6			X			X	
Removal of arterial catheter	11.3.2							X
Discharge from research clinic								X
Baseline symptoms	11.2.10	X		X				
Adverse events	11.4.2							----- X -----
Prior and concomitant medications	11.2.6							----- X -----

CSP= Clinical Study Protocol, HIV= Human Immunodeficiency Virus, ECG= Electrocardiogram

1. Timepoints given for Visit 2 are approximate and may be adjusted over the day if needed for logistical reasons in agreement between the research clinic and the PET-Centre.
2. Or after early withdrawal.
3. Confirmation of eligibility.
4. Activities performed at the PET-Centre

8.1.2 **PART B: PET 3**

In PART B of the study, two different formulations of [¹¹C]nicotine will each be given to 2 subjects. The subjects will have one PET-assessments each (PET 3) after two inhalations of [¹¹C]nicotine via the *myblu*™.

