PART B will be completed for 2 subjects on each formulation before a decision will be taken if 3 additional subjects should be added to PART B. The decision is based on whether the results from the first scans show significant, quantifiable uptake of radioactivity in the brain. If 3 additional subjects are included, they will be treated with the formulation that showed the best uptake profile.

The IP will be given as inhalation (“puffs”) via the *myblu*™ e-cigarette system to obtain a tracer dose of up to 50 MBq.

Subjects will come for 2 visits to the clinic, 1 MRI assessment visit (if not on the PET assessment day) and have 1 End-of Study follow-up telephone call (Visit 3).

Screening (Visit 1) will take place from Day -28 to Day -1 and will include an eligibility check, review of health status and inhalation training, see Table 8.1-2 for details.

At Visit 2, subjects will arrive to the clinic in the morning of Day 1 and will remain at the clinic until the afternoon. Day 1 will contain pre-PET safety assessment, preparation for the PET assessments (including insertion of an arterial catheter), one PET assessment session and safety follow-up (including removal of arterial catheter) after the PET assessment.

The subjects will have breakfast (optional) at the research clinic before the PET-session. Lunch (optional) will be served at the research clinic after the PET session.

The subjects will be carefully monitored by clinical staff during and after the PET-session. There is immediate access to equipment and qualified staff in case of emergency.

A final End-of-Study phone call (Visit 3) will take place on Day 7 (± 2) or after early withdrawal to follow up on safety (AEs and concomitant medications).

During the study period, the subjects will also have an MRI-scan. The MRI can be performed at any suitable timepoint during the study after the screening visit until the End-of-Study-visit.

Each subject is expected to participate in the study for approximately 7 days from the day of PET-session (Day 1, Visit 2) to the End-of Study Visit. The Screening Visit will be performed within 28 days prior to PET-scanning (Day -28 to Day -1).

The schedule of events is shown in Table 8.1-2.

Study assessments are described in Section 11.

Table 8.1-2 Schedule of events PART B

Visit	Refer to CSP section:	Visit 1 Screening	Visit 2 ¹			Visit 3 End-of- study
			Day -28 to Day -1	Admission 08:00	Day 1	
Assessment/ Approximate timepoints						Phone call

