11.4 Assessments related to secondary endpoints

11.4.1 *PET endpoints*

Refer to Section 11.3.

11.4.2 *Adverse events*

The Principal Investigator is responsible for ensuring that all medical staff involved in the study is familiar with the content of this section and the content of the CTC standard operating procedures (SOPs) regarding handling of AEs.

11.4.2.1 *Definition of adverse event*

An AE is defined as any untoward medical occurrence in a subject administered an IP and which does not necessarily have a causal relationship with this treatment. An AE can therefore be any unfavourable and unintended sign (including clinically significant abnormal values from relevant tests, such as clinical safety laboratory tests, ECGs, vital signs), symptom, or disease temporally associated with the use of an IP, whether or not considered related to the IP.

11.4.2.2 *Definition of serious adverse event*

An SAE is any AE which:

- results in death
- is life-threatening (this refers to a reaction in which the subject was at risk of death at the time of the reaction; it does not refer to a reaction that hypothetically might had led to death if the reaction was more severe)
- requires in-patient hospitalisation or prolongation of existing hospitalisation
- results in persistent or significant disability/incapacity
- is a congenital anomaly/birth defect
- is an important medical event (IME) (this refers to a reaction that may not be immediately life-threatening or result in death or hospitalisation, but may jeopardise the subject or may require intervention to prevent any of the other outcomes defined above)

Examples of IMEs are intensive treatment in an emergency room for allergic bronchospasm or blood dyscrasias, convulsions that do not result in hospitalisation, development of drug dependency, and drug abuse.

Planned hospitalisations or surgical interventions for a condition that existed before the subject signed the ICF and that did not change in intensity are not SAEs.

If there is any doubt as to whether an AE meets the definition of an SAE, a conservative viewpoint must be taken, and the AE must be reported as an SAE.

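### Post-product vital signs are judged against a screening reading 1-28 days old with no required nicotine abstinence, and no pre-product reading on Day 1 is legible in the schedules

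*Protocol*

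**What the plan says.** - **AE rule (11.4.3).** Each reading is classified: "Vital signs will be judged as normal, abnormal, not clinically significant or abnormal, clinically significant". A change criterion with a named comparator follows: "Post-IP vital signs, where the change from the values measured at the screening visit is judged as" abnormal and clinically significant are reported as AEs.
- **Age of the comparator (8.1.1, 8.1.2).** "The Screening Visit will be performed within 28 days prior to PET-scanning (Day -28 to Day -1").
- **Nicotine (9.4, 9.6.1).** Subjects are daily smokers. Nicotine products other than the IP are barred from midnight before the PET assessment until the subject leaves the clinic. The lead-in to 9.6 applies the restrictions from screening onward, but the nicotine item sets its own, narrower window.
- **Day 1 content.** For Part B, 8.1.2 states: "Day 1 will contain pre-PET safety assessment, preparation for the PET assessments (including insertion of an arterial catheter"). 8.1.1 and the synopsis say much the same, and none of them itemises the safety assessment. The synopsis entry "Safety assessments" lists AEs and vital signs for the study as a whole.
- **Analysis (17.1, 17.6.2).** Baseline is the visit holding the last data collection before the first IP. Vital signs are tabulated as absolute and percent change from it.
- **Endpoint (7.2.1, 7.3.1).** Clinically significant change in vital signs is secondary in Part A and exploratory in Part B.

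**The concern.** The endpoint is a change, so its meaning depends on the reference value. The reference named in 11.4.3 was taken on another day, and possibly soon after a cigarette. The later reading is taken under abstinence apart from the IP. In a study of a nicotine product, a difference in nicotine state between the two readings bears directly on what is being measured.

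Two further features add to this. First, 17.1 names a visit rather than a reading, and Visit 2 also contains the post-IP vital signs. Even if Visit 2 is meant, no single pre-IP value is identified. Second, events between consent and catheter insertion count as baseline symptoms (11.2.10), and AEs are collected only from insertion (11.4.2.3). Without a reading on Day 1 before IP, the site cannot tell whether a shift since screening arose before or after that boundary.

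This is not a detail for the SAP to settle. An SAP can choose among collected values but cannot supply one that was never taken.

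**Working it through.** The protocol gives no figure for the shift, so there is none to reproduce. The check is day and hour arithmetic, the position of marks in the schedules, and the two possible readings of the text.

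**Age of the comparator.** With no Day 0, Day -28 is 28 days before Day 1 and Day -1 is 1 day before. The range is 1-28 days.

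**Required abstinence.**
- At screening: 0 h.
- At Day 1 admission: 00:00 to 08:00 = 8 h, taking midnight as the one that begins Day 1. An earlier midnight would make it longer. Clock times in the schedules are approximate.
- At a Part A reading after the 14:00 session: more than 14 h, apart from the IP.

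**Marks in the schedules.** The columns are flattened and the headers misaligned: the last field, headed Visit 3, also holds PET 2, catheter removal and discharge. Only the order of marks between rows is used. Field numbers count from the left, with the row label as 1.

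| Row | Table 8.1-1 (Part A) | Table 8.1-2 (Part B) |
|---|---|---|
| Vital signs | 3, 9 | 3, 7 |
| Catheter insertion (admission position) | 5 | 5 |
| PET and IP administration | 6, 9 | 6 |
| Catheter removal, discharge | 9 | 7 |

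In each table 8 rows carry a mark at the admission position (field 5): eligibility confirmation, alcohol test, drug screen, optional inhalation training, Allen test, catheter insertion, meals and baseline symptoms. Vital signs is not among them. Its only mark after screening shares its position with catheter removal and discharge, which comes after the first IP administration in both parts.

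**Reading 1: no vital signs on Day 1 before IP.** The last vital-sign collection before IP is screening. 11.4.3 and 17.1 then agree, and both point to a value 1-28 days old without required abstinence. The change in 17.6.2 combines any product effect with between-day and smoking-state differences, and nothing collected can separate them.

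**Reading 2: the safety assessment before PET includes vital signs.** 17.1 then points to Visit 2 for the tabulation, while 11.4.3 keeps screening for AE judgement. One post-IP value is compared with two references, and the schedules do not show the reading.

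**Subjects affected.** 10 in Part A plus 4 to 7 in Part B = 14-17.

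**Room on the Day 1 morning (Part A).** 08:00 admission to 10:00 PET is 120 min; less 30 min for transfer (11.3.4) leaves 90 min. Ten minutes of supine rest is 10/90 = 11% of that, shared with the 8 items above.

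**The case against.** A reader might infer that 11.4.3 flatly contradicts 17.1. The document does not support that. If no Day 1 reading before IP is planned, the two sections agree. If one is planned, the mismatch lies between an AE-reporting rule applied by investigator judgement and a tabulation rule, so it is a difference of reference value and not a contradiction within one rule. The evidence that a reading is intended is also thin. The synopsis list covers the whole study, and the items marked at admission could make up the safety assessment by themselves.

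The absence of a Day 1 mark is inferred from damaged tables. The inference is plausible because the pattern is the same in both, but it is not a stated fact.

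It might also be inferred that clinically significant abnormal vital signs would go unreported. They would not: the AE definition in 11.4.2.1 includes "clinically significant abnormal values from relevant tests, such as clinical safety laboratory tests, ECGs, vital signs", whatever the comparator. Only changes among values not judged abnormal could be missed or misread. In an open-label study the investigator can weigh abstinence and elapsed time when judging them.

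Finally, a morning baseline does not fully cure the problem. Abstinence continues all day, so the two Day 1 readings would still differ by some 6 hours in Part A (14 - 8). The post-IP reading may also come well after the puffs, since 6.3 keeps subjects at least 2 hours after administration.

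All of this limits the consequence. None of it makes screening a sound reference for a change endpoint.

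**Conclusion.** The point holds with limited consequence and should be put right. That 11.4.3 uses a comparator 1-28 days old, without required abstinence, is plain from the text. That 17.6.2 rests on the same value depends on the schedules having no Day 1 mark before IP, as they appear to. If the original tables or the intended safety assessment do include such a reading, what remains is the mismatch between 11.4.3 and 17.1.

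Neither the size nor the direction of the shift can be computed from the document. The effect is confined to a descriptive vital-sign table, with 5 subjects per formulation in Part A and initially 2 in Part B, and to the change-based AE rule. A shift common to both formulations would largely cancel between them. The primary PET endpoints are unaffected.

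**What to change.** - Mark one supine blood pressure and pulse reading on Day 1 before the first IP administration in Tables 8.1-1 and 8.1-2, or confirm that the safety assessment before PET already includes it.
- Take it at the same point relative to catheter insertion in every subject.
- Name that reading, not the visit, as the vital-sign baseline in 11.4.3, 17.1 and 17.6.2.
- Keep the screening values for exclusion criterion 7.

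**Cost.** About 10 minutes of supine rest on a morning that is already busy, though footnote 1 to both tables allows times to be adjusted; one mark in each schedule; and baseline wording in three sections.

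**What it buys.** It removes the between-day difference and reduces the smoking-state difference without removing it. With no control, it does not isolate the product from catheter, scan, coffee or meal effects, and the report should not present the change as a product effect alone.
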